## 5.2 Packaging, Labeling, Storage

Packaging and labeling will be performed in strict accordance with the local regulatory specifications and requirements.

The packaging and labeling of gadopiclenol will be performed by Guerbet.

In addition to the usual and regulatory labeling for clinical studies, each IMP will have a white detachable sticker indicating the protocol number, batch ID, IMP number and patient ID number. This label will be stuck on the patient file or trial documentation for tracking purpose.

IMP will consist in one box that contains one 10-mL vial with 3mL of gadopiclenol.

In case of damaged IMP, a new IMP will be allocated to the patient via the IWRS.

All IMPs will be stored in a secure place, under the responsibility of the Investigator or other authorized individual and under the conditions described in the Investigator's Brochure. The IMPs should be stored at a temperature of 25°C or below in the original package, protected from light and not frozen.

At the time of the trial completion, all used (including empty vials) and unused IMPs should have been returned to the Sponsor or to the predefined location for storage before destruction. Destruction at site can be considered as an option if it is expressly authorized by Guerbet and subject to the reconciliation validated by Guerbet.

## 5.3 Condition of Investigational Medicinal Product Allocation

### 5.3.1 *Investigational Product Allocation*

A central web randomization system or IWRS (Interactive Web Response System) will be used to manage inclusion of patients in the trial, allocation of sampling time points (one of 4 within each time window as per [Table 1: Sampling time points randomly allocated.](#)) and IMP allocation. Once eligibility criteria are confirmed, Patient Identification Number will be recorded into the system.

IWRS will ensure a balanced distribution of the trial population between 3 predefined age groups as following:

- Group 1: at least 20 patients aged 3 to 23 months (inclusive)
- Group 2: at least 12 patients aged 28 days to less than 3 months
- Group 3: at least 5 patients aged from birth to 27 days (term newborns)

IWRS will ensure that at least 25 patients (50%) are scheduled for contrast-enhanced MRI of CNS.

The first enrollment in the age group 2 was conditioned by the decision of the first TSRB. Based on the good safety profile of gadopiclenol, following amendment 2, the inclusions in the age group 3 will be opened simultaneously to inclusions in age groups 1 and 2. The inclusions will continue until the overall number reaches 50 patients.

IMP number will be independent from the Patient Identification Number.

The dose of gadopiclenol to be administered will be rounded to one decimal and calculated based on patient's BW with one decimal fraction.

In case of problem of IMP allocation (e.g. wrong IMP administered to a patient), the site must immediately report the incident to Guerbet and the IWRS provider in order to ensure that all corrective actions are taken. Corrective actions may include transferring the IMP to quarantine to prevent further

 CONFIDENTIAL	Protocol No. GDX-44-015 Version No. 4.0 including amendments 1 & 2 & 3 Date 09 Oct 2023	F015919-05 Page 36 / 75
--	---	----------------------------

IMP allocation by the site until the situation is under control again. Detailed instructions can be found in the IWRs manual provided to the sites.

### **5.3.2 Double-Blind Conditions**

Not applicable. The IMP will be administered in an open-label fashion.

### **5.3.3 Individual Trial Treatment Unblinding**

Not applicable.

## **5.4 Investigational Medicinal Product Management**

The Investigator, the hospital pharmacist, or other personnel allowed to store and dispense IMP(s) is responsible for ensuring that the IMP used in the clinical trial is securely maintained as specified by Guerbet and in accordance with the applicable regulatory requirements.

Any quality issue noticed with the receipt or use of an IMP (deficient IMP in condition, appearance, pertaining documentation, labeling, expiry date, temperature excursion, etc.) should be promptly notified to Guerbet, who will initiate a complaint or deviation procedure.

Under no circumstances shall the Investigator supply IMP to a third party, allows the IMP to be used other than as directed by this clinical trial protocol, or dispose of IMP in any other manner.

## **5.5 Auxiliary Medicinal Product and Other Trial Products**

Not applicable.

## **5.6 Trial Product Compliance and Accountability**

A third party, the Investigator, the hospital pharmacist, or other allowed personnel, designated by the Investigator, will keep accurate records of IMPs accountability at site level as well as accurate records of the batch numbers and quantities of the IMP given to each patient.

The dosing information will be recorded in individual patient's records. It is recommended not to discard immediately the injection material (syringe, tubing) but to keep them at site for one week to investigate the IMP administration conditions if necessary. When protocol required IMP administration conditions are not followed, reason(s) will be given and recorded by the Investigator in patient's source document and electronic Case Report Form (eCRF).

 CONFIDENTIAL	Protocol No. GDX-44-015 Version No. 4.0 including amendments 1 & 2 & 3 Date 09 Oct 2023	F015919-05 Page 37 / 75
--	---	----------------------------

## 6 CONCOMITANT MEDICATIONS / PROCEDURES

### 6.1 Concomitant Medications

Any medication, including homeopathic products, pre-medication, over-the-counter medications, as well as prescription drugs, on-going at the time of patient's parent(s) or legal guardian (where applicable) informed consent signed or administered until V4 (1-week safety follow-up) will be recorded in the patient's eCRF.

Between V4 and V5 safety visits, newly started concomitant medications/treatments in patients experienced at least one AE will be documented. Any GBCA injection will be documented in all patients.

The following information must be provided:

- Drug (brand name or generic name)
- Route of administration
- Purpose (medical history/trial disease/AE/pre-medication/prophylaxis)
- Indication
- Start/end period.

#### 6.1.1 *Concomitant Medications of Special Attention*

In order to limit any interference with the safety and efficacy evaluation of Investigational Product, the following precaution and restriction must be considered:

Currently, no treatment has been identified that can prevent an allergic reaction with any GBCA. Thus, no pre-treatment of any nature will be recommended before contrast-enhanced MRI. Nevertheless, if the Investigator decides to premedicate a patient, the treatment must be documented in the medical file and then in the eCRF. Treatments used for general sedation or topical anesthesia or other non-pharmacological methods (using feed and swaddle, etc.) will be set up according to the current practice at site.

In general, there are no specific recommendations regarding GBCA, and therefore, no specific hydration procedure is defined in this protocol. Nonetheless, whenever possible, the patient's parents or legal guardian (where applicable) should be instructed to give a patient to drink water and other fluids liberally before and after the injection.

According to current knowledge, there is no other concomitant treatment of special attention in that trial. However, warnings and precautions for use of the concomitant treatments taken by the patient should be considered.

#### 6.1.2 *Prohibited Concomitant Medications*

A minimum of 1-week wash-out is required between any other contrast agent administration for CT and/or MRI and gadopiclenol injection. At least 1 week must elapse between trial contrast-enhanced MRI and any subsequent contrast agent administration.

Any medication preceding or subsequent to the gadopiclenol administration that would alter gadopiclenol pharmacokinetic parameters (e.g., treatment with diuretics), is not permitted.

Any change in chemotherapy is prohibited within 1 day prior to and 1 day after gadopiclenol administration.

Guerbet    CONFIDENTIAL	Protocol No. GDX-44-015 Version No. 4.0 including amendments 1 & 2 & 3 Date 09 Oct 2023	F015919-05 Page 38 / 75
--	---	----------------------------

## 6.2 Concomitant Procedures

Any procedure performed during the trial and related to any reported AE will be recorded in the patient eCRF. At least the following information must be provided:

- Name of procedure
- Indication
- Duration

Any intervention that would prevent from obtaining the required blood samples or performing other trial procedures (e.g., surgery) is not permitted between the screening visit and up to 1 day after gadopiclenol administration.

Any procedure preceding or subsequent to the gadopiclenol administration that would alter gadopiclenol pharmacokinetic parameters (e.g., blood transfusion), is not permitted.

 CONFIDENTIAL	Protocol No. GDX-44-015 Version No. 4.0 including amendments 1 & 2 & 3 Date 09 Oct 2023	F015919-05 Page 39 / 75
--	---	----------------------------

## 7 EVALUATION CRITERIA

### 7.1 Primary Criteria

Gadopiclenol pharmacokinetics in plasma for pediatric patients aged up to 23 months (inclusive) will be assessed based on the following pharmacokinetic parameters determined from the population PK model:

- Simulated concentrations at 10, 20 and 30 minutes post injection
- Area Under the Curve,
- Elimination half-life,
- Total clearance,
- Volume of distribution.

Gadopiclenol concentrations in plasma will be determined using a validated liquid chromatography coupled with tandem mass spectrometry (LC-MS/MS) method.

A separate bioanalytical protocol will describe the gadopiclenol assays in plasma samples. Those assays will be performed by Eurofins ADME BIOANALYSES, [name].

### 7.2 Secondary Criteria

#### 7.2.1 *Clinical and biological safety*

- Physical examination at visits 1, 2 (if applicable), 3, 4 and 5 including examination of general appearance, skin (including extremities), neck (including thyroid), eyes, abdomen, back, lymph nodes, peripheral vascular and neurological examination and other (any other observed abnormalities).  
Any clinically significant abnormality or change will be recorded as AE or medical history if examination performed prior to IMP administration upon Investigator's judgement.
- Vital signs (temperature, systolic and diastolic blood pressure, pulse rate and peripheral oxygen saturation (SpO2)) at 3 time points: prior to IMP injection, 10-60 min and 1 day after IMP injection.

Body temperature will be measured on forehead by infrared thermometer.

Blood pressure and pulse rate will be measured after a rest for at least 5 minutes in supine position. Blood pressure will not be measured on the arm used for the injection.

Peripheral oxygen saturation (SpO2) will be measured by pulse oximetry using a transcutaneous non-invasive light emitter.

If significant change in vital signs occurs, vital signs should be measured more frequently as long as necessary to ensure that the change has been resolved and/or that the subject is stable. Any clinically significant abnormality or change will be recorded as AE or medical history if vital signs performed prior to IMP administration upon Investigator's judgement.

- Safety laboratory variables centrally analyzed (biochemistry and hematology) from blood samples collected at screening and 1 day after IMP injection.

 CONFIDENTIAL	Protocol No. GDX-44-015 Version No. 4.0 including amendments 1 & 2 & 3 Date 09 Oct 2023	F015919-05 Page 40 / 75
---	---	----------------------------

- Hematology: red blood cells (RBCs), white blood cells (WBCs) counts: neutrophils, eosinophils, basophils, lymphocytes and monocytes, platelet count, hemoglobin, hematocrit, mean red blood cells volume (MCV).
- Biochemistry: sodium, potassium, chloride, blood urea nitrogen (BUN), creatinine, total protein, calcium, phosphorus, iron, ferritin, transferrin, total bilirubin, conjugated bilirubin, aspartate amino transferase (AST), alanine amino transferase (ALT), alkaline phosphatase, lactate dehydrogenase (LDH), PT (prothrombin time) / INR (International Normalised Ratio).
- Estimated glomerular filtration rate (eGFR) calculated by central lab based on the bedside Schwartz equation prior to and 1 day after IMP injection.

Bedside Schwartz equation [\[2222-24\]](#) will be used with creatinine methods with calibration traceable to isotope dilution mass spectroscopy (IDMS):

$$\text{eGFR (mL/min/1.73 m}^2\text{)} = (0.413 \times \text{Height in cm}) / \text{Standardized Serum creatinine (mg/dl)}$$

Post-contrast acute kidney injury (PC-AKI) is defined as an increase in sCr of  $\geq 0.3$  mg/dl or sCr  $\geq 1.5$  times baseline. Such changes will be monitored, and additional information may be requested to the Investigator.

Any clinically significant abnormal value or change will be recorded as AE. Any abnormal value on sampling performed prior to IMP administration could be recorded in medical history upon Investigator's judgement.

- Tolerance at the injection site (eruption, extravasation and inflammation) at 3 time points: during injection, 10-60 min and 1 day after IMP injection.
- Adverse events (AE) occurred from the beginning of patient's participation in the trial (Informed Consent Form signature) until the end of the participation.
- Clinical examination for active detection of Nephrogenic Systemic Fibrosis (NSF) at 3-month follow-up safety visit. In case of suspicion of NSF a deep skin biopsy will be performed.

### 7.2.2 *Gadopiclenol-enhanced MRI (Pre and Paired (pre+post)) efficacy evaluation*

Gadopiclenol-enhanced MRI efficacy will be assessed by on-site radiologist for both pre-contrast (Pre) and pre+post contrast (Paired) images, based on following parameters:

- Technical adequacy for diagnosis using a 4-point scale: poor, fair, good or non-diagnostic  
If non-diagnostic, reasons will be provided:
  - 1 = Artifacts due to patient
  - 2 = Artifacts due to machine
  - 3 = Injection technical failure
  - 4 = Inadequate anatomic coverage
  - 5 = Other, please specify
- Assessment of overall contrast quality using a 5-point scale: 1= None (for example, in case of a non-enhancing lesion), 2= Poor, 3= Moderate, 4= Good, 5= Excellent.
- Number and location of lesions/abnormal vessels and largest diameter (lesions only) of three most representative lesions/abnormal vessels will be recorded.

 CONFIDENTIAL	Protocol No. GDX-44-015 Version No. 4.0 including amendments 1 & 2 & 3 Date 09 Oct 2023	F015919-05 Page 41 / 75
---	---	----------------------------

- Quantitative assessment (not applicable for vessels): percentage of enhancement (E%) and Lesion to Background Ratio (LBR) and Contrast to Noise Ratio (CNR) for CNS only for up to 3 most representative lesions (largest enhancing lesions).
- **Percentage of enhancement (E%) of lesion** will be calculated by using the equations below:

$$E\% = \frac{SI_{post} - SI_{pre}}{SI_{pre}} \times 100$$

where  $SI_{post}$  = SI of lesion on post injection T1 weighted images;

$SI_{pre}$  = SI of lesion on pre injection T1 weighted images.

- Measurements of the signal intensity (SI) of the lesion will be performed on the pre and post-injection identical T1 weighted sequences.
- **Lesion to Background Ratio on post-injection T1 weighted images (LBRpost)** will be calculated by using the equations below:

$$LBR_{post} = \frac{SI_{post}}{SI_b}$$

where  $SI_{post}$  = SI of lesion on post injection T1 weighted images;

$SI_b$  = SI of background (surrounding healthy tissue of the lesion) on post injection T1 weighted images.

- **Contrast to Noise Ratio on post-injection T1 weighted images (CNRpost) for CNS only**

$$CNR_{post} = \frac{SI_{post} - SI_{ht}}{SD_{noise}}$$

where  $SI_{post}$  = SI of lesion on post injection T1 weighted images;

$SI_{ht}$  = SI of surrounding healthy tissue in brain or spinal cord on post injection T1 weighted images;

$SD_{noise}$  = Standard Deviation (SD) of background noise on post injection T1 weighted images.

- Measurements of the SI of the lesion are to be made on the best representative images of the pathology. The ROI for a lesion will encompass a homogeneous area within the lesion as large as possible.
- For healthy tissue measurements, ROI should be placed in normal appearing homogeneous brain or spinal cord.
- Measurements of the background noise SD are to be placed on the slice where corresponding lesion is located. The ROI should be placed outside head or spine but within imaging FOV.
- Lesion/vessel visualization (border delineation, internal morphology and degree of contrast enhancement) using a 4-point scale for each parameter.

The Investigator will record each of lesion/vessel visualization parameters (lesion border delineation, internal morphology and degree of contrast enhancement) for up to 3 most representative lesions or vessel abnormalities.

- Border delineation:

Delineation of the lesion/vessel border is defined as the distinction of lesion or vessel from surrounding tissues. This criterion will be assessed through the following scale:

- 1 = none: no or unclear delineation
- 2 = moderate: some areas of clear delineation but also with some significant areas of non-distinct delineation
- 3 = good: almost clear but not complete delineation
- 4 = excellent: border outline is sharp with clear and complete delineation
- Internal morphology:

Internal morphology of the lesion or vessel includes an identification of lesion architecture and the internal features and homogeneity of vessel enhancement. This criterion will be assessed through the following scale:

- 1 = poor: poorly seen
- 2 = moderate: majority of lesion or vessel is poorly seen
- 3 = good: majority of lesion or vessel is clearly seen but with minor parts of lesion or vessel invisible
- 4 = excellent: lesion or vessel is well seen.

- Degree of contrast enhancement:

This criterion will be a qualitative assessment according to the following scale:

- 1 = no: lesion or vessel is not enhanced
- 2 = moderate: lesion or vessel is weakly enhanced
- 3 = good: lesion or vessel is clearly enhanced
- 4 = excellent: lesion or vessel is clearly and brightly enhanced
- Change in diagnosis from Pre to Paired MRI: yes/no/not assessable
- Change in diagnostic confidence from Pre to Paired MRI, defined as the degree of confidence that the information on the images represents the true and complete clinical picture of a patient: yes/no/not assessable

The diagnostic confidence will be assessed through the following scale:

- 1 = nil: very uncertain
- 2 = poor: uncertain
- 3 = moderate: moderately certain
- 4 = high: good certainty
- 5 = excellent: very certain

When the investigator chooses 'not assessable' for diagnosis, by definition the confidence level is 1 (= very uncertain).

- Change in treatment plan from Pre to Paired MRI: yes/no/not assessable

The Investigator will document therapeutic management proposed based on both pre-contrast (Pre) and pre+post contrast (Paired) MRI (surgery, biopsy, chemotherapy, radiotherapy, other treatment)

 CONFIDENTIAL	Protocol No. GDX-44-015 Version No. 4.0 including amendments 1 & 2 & 3 Date 09 Oct 2023	F015919-05 Page 43 / 75
---	---	----------------------------

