  - Lesion/vessel visualization (border delineation, internal morphology and degree of contrast enhancement) for up to 3 most representative lesions or vessel abnormalities using a 4-point scale for each parameter.

- Change in diagnosis from Pre to Paired MRI.
- Change in diagnostic confidence from Pre to Paired MRI. Diagnostic confidence is assessed using a 5-point scale: 1 = nil: very uncertain, 2 = poor: uncertain, 3 = moderate: moderately certain, 4 = high: good certainty, 5 = excellent: very certain
- Change in treatment plan from Pre to Paired MRI.

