### 11.3.7 *Efficacy Analyses*

All efficacy analyses will be done using the FAS and summarized per cohort and overall:

- Technical adequacy for diagnosis: results will be tabulated qualitatively for Pre and Paired (pre+post contrast) images. Shift tables between Pre and Paired scores will be provided.
- Assessment of overall contrast quality score will be tabulated qualitatively for Pre and Paired images. A shift tables between Pre and Paired scores will be provided.
- Evaluation of lesions/abnormal vessels: number and locations of detected lesions/abnormal vessels, and largest diameter (lesions only) of the 3 most representative lesions/abnormal vessels will be tabulated qualitatively and quantitatively respectively for Pre and Paired images.
- Assessment of contrast quality: signal intensity of lesion, percentage of enhancement (E%), LBR and CNR will be tabulated quantitatively.
- Lesion /vessel visualization (border delineation, internal morphology and contrast enhancement): for each parameter, score will be tabulated qualitatively for Pre and Paired images. A shift tables between Pre and Paired scores will be provided.
- Diagnosis (only for Pre MRI), diagnostic confidence, treatment plan for Pre and Paired MRI, change in diagnosis, change in diagnostic confidence and change in treatment plan from Pre to Paired MRI will be tabulated qualitatively.

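### Change in diagnostic confidence is recorded without direction and has no shift table, so the planned tables cannot in general separate patients who gained confidence from patients who lost it

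*Protocol*

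**What the plan says.** The synopsis (Secondary criteria) ties the change in confidence to an ordered score: "Diagnostic confidence is assessed using a 5-point scale: 1 = nil: very uncertain", rising to 5 for very certain. Protocol 7.2.2 repeats the scale but gives the change three unordered answers, for the confidence that the images' information "represents the true and complete clinical picture of a patient: yes/no/not assessable". It defines confidence itself. It does not say what size or direction of movement makes a 'yes'.

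The same section adds a scoring rule: "When the investigator chooses 'not assessable' for diagnosis, by definition the confidence level is 1 (= very uncertain". It also lists a neighbouring endpoint, "Change in diagnosis from Pre to Paired MRI: yes/no/not assessable".

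For the analysis, Protocol 11.3.7 lists "Diagnosis (only for Pre MRI), diagnostic confidence, treatment plan for Pre and Paired MRI, change in diagnosis, change in diagnostic confidence". The list closes with the corresponding item for the treatment plan, and everything on it is to be tabulated qualitatively. For technical adequacy the same section says "Shift tables between Pre and Paired scores will be provided", and it makes the same provision for overall contrast quality and for lesion/vessel visualization. It names no shift table for diagnostic confidence.

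**The concern.** Confidence is one of the patient-level measures of diagnostic impact under secondary objective 2. A reader will take a percentage with changed confidence as a percentage helped by contrast. As coded, a patient who goes from 4 to 2 adds to that percentage just as one who goes from 2 to 4 does.

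The analysis is descriptive only (Protocol 11.1), so the tables are the result: no planned model or test will restore the direction. Three other ordered Pre/Paired scores get a shift table, and no reason is given for treating confidence differently.

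**Working it through.** The documents give no expected rate, power or threshold for this endpoint, so there is no planned figure to reproduce. The check is whether the planned output can tell gains from losses.

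**Inputs.** Confidence scale 1 to 5 and the yes/no/not assessable coding (Protocol 7.2.2). Separate Pre and Paired tabulation of confidence, as 11.3.7 is most naturally read. Efficacy is analysed in the FAS, that is, all patients with an enhanced MRI (11.3.2, 11.3.7). I take all 50 planned patients to be in it. The score patterns below are assumptions.

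**Formulas.** Gains = patients with Paired > Pre. Losses = patients with Paired < Pre. 'Yes' = gains + losses.

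**Step 1: patterns that the Pre and Paired tables do separate.** All 50 patients start at 3.

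| Pattern | Gains | Losses | 'Yes' | Paired distribution |
|---|---|---|---|---|
| 20 go 3→4 | 20 | 0 | 20/50 = 40% | 3: 30, 4: 20 |
| 10 go 3→4, 10 go 3→2 | 10 | 10 | 20/50 = 40% | 2: 10, 3: 30, 4: 10 |

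The change endpoint is the same in both rows, but the Paired distributions differ, so the planned output separates them.

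**Step 2: patterns that they do not separate.** In both, 35 patients stay at 3.

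| Pattern | Gains | Losses | 'Yes' | Pre | Paired |
|---|---|---|---|---|---|
| 5 each 2→3, 3→4, 4→2 | 10 | 5 | 15/50 = 30% | 2: 5, 3: 40, 4: 5 | 2: 5, 3: 40, 4: 5 |
| 5 each 3→2, 4→3, 2→4 | 5 | 10 | 15/50 = 30% | 2: 5, 3: 40, 4: 5 | 2: 5, 3: 40, 4: 5 |

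Every planned confidence table is the same for the two patterns, yet one has twice as many gains as losses and the other the reverse. Net movement is zero in both: 5×1 + 5×1 − 5×2 = 0 in the first, and the same with signs reversed in the second. A signed change or a shift table separates them at once.

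**Step 3: the side issue on change in diagnosis.** Section 7.2.2 gives no coding for a patient who is not assessable on Pre but diagnosed on Paired. Assume 5 clear changes among the other patients, plus m patients of this kind, in 50:

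| m | Coded no: 5/50 | Excluded: 5/(50 − m) | Coded yes: (5 + m)/50 |
|---|---|---|---|
| 5 | 10.0% | 5/45 = 11.1% | 10/50 = 20.0% |
| 10 | 10.0% | 5/40 = 12.5% | 15/50 = 30.0% |

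Because 11.3.7 tabulates diagnosis for Pre only, the tables would not show which coding had been used.

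**The case against.** **The Pre and Paired confidence tables already show direction.** This stands in part. They show net movement, and step 1 is a case where they suffice. A reader might infer that harm cannot be told from benefit at all, and the documents do not support that. What is lost is direction within patients, as step 2 shows.

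**The rule that sets confidence to 1 hides nothing.** This stands. A reader might infer that the rule conceals gains. It does the opposite: a patient not assessable on Pre and diagnosed with confidence 4 on Paired scores 1 then 4, and the gain is kept. The rule does leave one loose end. Because a not-assessable diagnosis always has a score, it gives no reason to code the change in confidence as not assessable, and that category needs its own definition.

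**Diagnoses made possible by contrast are not shown to be lost.** This stands. A reader might infer that such patients drop out of change in diagnosis. No section says so: the coding is undefined, and 'yes' is as open as 'not assessable'.

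**A separate clinical analysis plan may settle this.** Protocol section 11 defers full detail to a Statistical Analysis Plan. The SAP supplied covers population pharmacokinetics only and has no efficacy section. A shift table may therefore be specified elsewhere, which cannot be checked here. That would not remove the directionless coding written into 7.2.2.

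**The stakes are limited.** This stands. The endpoint is secondary, uncontrolled and read on site, and no inference is planned.

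**Conclusion.** The point holds in a narrow form. The coding of change in diagnostic confidence merges gains and losses, and no table named in 11.3.7 recovers them in general. In the assumed pattern of 50 FAS patients, 10 gains with 5 losses and 5 gains with 10 losses produce identical planned confidence output, with 'yes' at 15/50. The example shows what the tables cannot distinguish. It does not predict how many patients will lose confidence, and the documents give no figure for that.

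The conclusion rests on reading 11.3.7 as tabulating confidence at both reads, and on no separate clinical plan already adding a shift table.

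The missing coding rule for change in diagnosis is a secondary clarification. Sample size, safety and the primary pharmacokinetic analysis are unaffected.

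**What to change.** 1. In Protocol 7.2.2, or in the clinical analysis plan if there is one, derive change in diagnostic confidence from the two recorded scores (Paired minus Pre) as improved, unchanged or worsened, and define when it is not assessable.
2. In 11.3.7, add a 5×5 Pre-by-Paired shift table for diagnostic confidence, per cohort and overall, as for the other ordered scores.
3. As a clarification, state how change in diagnosis is coded, and with what denominator, when the diagnosis is not assessable on Pre but made on Paired, and report the number of such patients.

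Items 1 and 2 cost some wording and one table and use only scores the protocol already has recorded at both reads. Their downside is that some results now counted as 'yes' will be reported as worsened. Item 3 needs a written rule. The documents do not say that the Paired diagnosis is recorded as a separate item, so the sponsor should check that the data can support the rule. If a clinical analysis plan already contains items 1 and 2, it is enough to cite it and align 7.2.2.
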